8.1. Monitor Training

The designated monitors and/or representatives of the Sponsor will be trained to monitor study progress including but not limited to the protocol and eCRFs, and per the Monitoring Plan.

8.2. Site/Investigator Training

The Sponsor is responsible for providing training to the Investigator and appropriate clinical site personnel on the following topics:

- Protocol
- Electronic case report form (eCRF) data entry and management
- Procedure/Laboratory/other testing requirements
- DrugSorb-ATR device

8.3. Site Monitoring

Completed eCRFs will be verified by the monitor both in person at the investigational sites and remotely at regular intervals throughout the study. The Investigator will allow the monitor and/or representative of the Sponsor, and any regulatory body to review and inspect the study files, subject eCRFs, subject medical records and other related study documents as required. All eCRFs will be reviewed for completeness and clarity. Missing or unclear data will be investigated by the monitor and will be retrieved, clarified, and entered by study personnel as necessary throughout the study. CytoSorbents, Inc., or their authorized representative may request additional documentation from the Investigator such as physician procedure notes or physician written summaries when adverse events are observed and reported.

8.4. Regulatory Agency Inspection

If an Investigator is contacted by a regulatory agency regarding this study, the Investigator will notify the Sponsor or its designee immediately. The Investigator and research coordinator must be available to respond to reasonable requests and queries made during the inspection process. The Investigator must provide the Sponsor or designee with copies of all correspondence that may affect the review of the current trial (e.g., Form FDA 483, Inspectional Observations and Warning Letters). The Sponsor may provide needed assistance in responding to regulatory audits.

9. STUDY ASSESSMENTS AND PROCEDURES

An outline of study assessments, procedures, labs, and associated time windows is given in the **Schedule of Assessments** ([Table 6](#) in [Appendix 4](#)). Subjects will be evaluated through the Follow-up evaluation at 30 days post-operation. Assessments and procedures that are recorded as Standard of Care (SOC) within the **Schedule of Assessments** are outside of the CIP and are optional. They may be recorded if they are performed in accordance with SOC at the particular institution. Failure to record an assessment/procedure that is listed as SOC will not be a violation of protocol. Required assessments and procedures (not denoted as SOC) that are not completed or that are completed outside of the specified windows will be recorded as a protocol deviation ([Section 13.2, 13.3](#)).

Reference [Section 4.3](#) for the full list of study endpoints. These endpoints require assessment of clinical events and/or treatments, blood product transfusions, drainage volume, and laboratory parameters. Definitions of analysis populations and description of statistical analyses of endpoints are briefly described in [Section 11](#) and will be detailed in the Statistical Analysis Plan (SAP) for the study.

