All bleeding events are to be recorded as AE/SAEs by the Investigator or designee. Volume of blood loss and necessary transfusions will be documented in the corresponding eCRFs where applicable. In some cases, these events may contribute to the subject’s UDPB class. [35] Classifications are based on criteria/events occurring within the first postoperative day (as presented in [Table 1](#)) and will be determined based on the relevant data entered within the eCRFs.

Of note, UDPB counts transfusions of PRBCs, platelets, FFP, and Cryoppt beginning at chest closure. While intra-operative transfusions of these blood products prior to chest closure will be documented, they will not be counted as part of the UDPB classification or contribute to the primary endpoint. Preoperative transfusions are not counted in the UDPB classification. Transfusions of PCC and rFVIIa are counted beginning at the start of the procedure for UDPB. [35] Measurement of CTD volume begins at chest closure for UDPB classification. All subjects with events meeting criteria for UDPB classification of moderate, severe, or massive bleeding (Classes 2, 3 or 4) will be referred to the CEC for adjudication of UDPB bleeding class. Bleeding events occurring beyond the first postoperative day (i.e., not eligible for UDPB classification) will be adjudicated by the CEC for clinical severity. Details on the process for adjudication and relevant definitions are provided in the CEC Charter.

Postoperative Ischemic Events:

Postoperative ischemic events occurring during the index hospitalization will be captured as safety

endpoints in this study. This is with the intent of evaluating any potential risk for ischemic rebound in the setting of rapid antithrombotic drug removal. Postoperative ischemic events include myocardial infarction (MI), stroke, and urgent coronary revascularization. Of note, given the occasional complexities of distinguishing ischemic from hemorrhagic stroke (i.e., ischemic with hemorrhagic conversion), *all* postoperative strokes occurring during the index hospitalization will be captured within the safety endpoint.

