All reported safety events occurring within 30 days of the study procedure that meet programmed criteria for cardiac ischemia or stroke will be submitted to the CEC for endpoint adjudication. All coronary revascularization procedures (regardless of open or percutaneous) that occur post-index procedure and during the follow-up period will be adjudicated by the CEC for the potential safety endpoint of *urgent coronary revascularization*. Details on endpoint definitions, adjudication criteria, and all other CEC processes/procedures are detailed in the CEC charter.

Venous Thromboembolic Events:

Postoperative venous thromboembolic events (VTEs) occurring during the index hospitalization will also be captured as safety endpoints in this study. These include clinically significant deep vein thromboses and pulmonary embolism. The intent is to identify any potential risk for thrombotic rebound in the setting of rapid anticoagulant removal.

All reported safety events occurring within 30 days of the study procedure that meet programmed criteria for VTE will be submitted to the CEC for endpoint adjudication. In addition to confirmation of VTE, the events will be evaluated by the CEC for clinical significance. Details on endpoint definitions, adjudication criteria, and all other CEC processes/procedures are detailed in the CEC charter.

Postoperative Mortality or AEs Resulting in Death

All deaths (including AEs resulting in death) that occur within 30 days of the study procedure will be adjudicated by the CEC for endpoint criteria. This includes assessment of the timing and nature of the mortality (cardiac vs. non-cardiac death). *For the purposes of this study, fatal bleeding will be considered a type of cardiac death.* Details on endpoint definitions, adjudication criteria, and all other CEC processes/procedures are detailed in the CEC charter.

Safety Reporting to the FDA

The Sponsor will provide safety reports (of adverse events, including relatedness to the device, severity, outcome/resolution, and all deaths) to the FDA for each set of 20 subjects enrolled. These reports are independent of the required annual reports for all IDEs.

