Appendix 2: Clinical Laboratory Evaluations

Clinical chemistry:	Hematology:
Alanine aminotransferase ^a Albumin ^a Alkaline phosphatase ^a Aspartate aminotransferase ^a Blood urea nitrogen Calcium Ionized Calcium ^a Chloride Creatinine Direct bilirubin ^a Gamma-glutamyl transferase ^a Glucose Potassium Sodium Total bilirubin ^a Total protein ^a	Hematocrit Hemoglobin Platelet count Red blood cell count White blood cell (WBC) count Differential ^a
Coagulation tests:	Other, including cardiac biomarkers
Coagulation Panel: Activated partial thromboplastin time International normalized ratio Prothrombin time Fibrinogen ^a Point of Care Test(s): Activated clotting time (ACT) [refer to Schedule of Assessments for specific timing of sampling]	Serum pregnancy test ^b Cardiac troponin (cTn) ^c

^a Performed only if part of routine standard of care. Sponsor agrees to forego the data if the assessments are not performed and recorded^b Performed in serum at Screening for all females of childbearing potential. Pre-consent test results done during the current admission MAY be used. Pre-consent test results done before the current admission MAY NOT be used.^c Performed in serum Screening for all females of child-bearing potential. Post-op testing will be per institutional standard of care, or as indicated by symptoms and concern for perioperative myocardial infarction

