- ⁿ All AEs will be recorded from point of authorization to participate in the study through the 30-day Follow-up. If an AE occurs, appropriate diagnostic and therapeutic measures are to be taken and the investigation treatment may be discontinued if deemed clinically necessary. Follow-up evaluations of the subject are to be performed until the subject recovers or until the clinical Investigator considers the situation to be no longer clinically significant. Serious AEs occurring after 30 days post-operation are to be reported to the Sponsor if, in the judgment of the Investigator, there is concern for potential association between the event and the use of the DrugSorb-ATR device.
- ^o If subject is intubated/requires mechanical ventilatory support, the maximum ventilation and mechanical support requirements will be recorded for each day.
- ^p Documented in the ABG eCRF; only required if the subject is intubated or on mechanical ventilatory support
- ^q The maximum vasopressor dosage will be recorded each day.
- ^r Physical exam performed on the day of screening as part of standard of care but occurring prior to signing of informed consent *may* be used for the screening PE. The physical exam and review of concomitant medication history will be repeated on the day of the procedure, if the day of the procedure is different than the day of screening
- ^s Assessments completed daily **through hospital discharge**.
- ^t In the advent of any cardiac ischemic AEs, EKG (to assess for Q waves) and cTn **must** be obtained. EKG will be provided as source documentation for CEC adjudication. cTn will be documented within the laboratory eCRF for CEC event adjudication
- ^u Through postoperative day 5 only.

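### Postoperative EKG and troponin results need not be entered and the adjudicators see only reported events, so an MI that is overlooked or judged not significant can stay out of the ischemic safety endpoint

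*Combined protocol and SAP*

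**What the plan says.** - **Endpoint.** Section 4.3.6 lists postoperative MI during the index hospitalization as an additional safety endpoint. Section 9.2.1 gives the reason for capturing ischemic events: "This is with the intent of evaluating any potential risk for ischemic rebound in the setting of rapid antithrombotic drug removal".
- **Schedule.** Table 6 (Appendix 4) requires EKG and troponin at Screening. After surgery both rows read SOC, with footnote t. Hematology, chemistry and coagulation, by contrast, are required from ICU admission through postoperative day 5.
- **Status of SOC items.** Section 9 says that they "are outside of the CIP and are optional". It continues: "They may be recorded if they are performed in accordance with SOC at the particular institution". And: "Failure to record an assessment/procedure that is listed as SOC will not be a violation of protocol".
- **Mandatory trigger.** Footnote t to Table 6 opens "In the advent of any cardiac ischemic AEs, EKG (to assess for Q waves) and cTn" and makes both tests compulsory in that case. The EKG then goes to the CEC as source, and the troponin goes into the laboratory eCRF.
- **Second trigger, troponin only.** Appendix 2 footnote c: "Post-op testing will be per institutional standard of care, or as indicated by symptoms and concern for perioperative myocardial infarction".
- **Route to adjudication.** Section 9.2.1 sends to the CEC "All reported safety events occurring within 30 days of the study procedure that meet programmed criteria for cardiac ischemia or stroke".
- **Partial backstop.** Section 9.2.1 also requires an abnormal change in a laboratory value to be recorded as an AE when the investigator classes it as clinically significant.

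**The concern.** The endpoint is meant to reveal a harm of rapid drug removal, but nothing guarantees that the data needed to see that harm enter the database. A site may run routine postoperative EKGs and troponins, leave the results unentered, and remain fully compliant. If nobody at the site recognises an ischemic event, no AE is reported, footnote t is not engaged, and the CEC has nothing to adjudicate.

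Two things are at stake. Missed events lower the MI count, which makes an absence of signal easier to reach in a trial of about 120 subjects. And what is captured depends on local testing and reporting habits, so the observed MI rate is hard to interpret.

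**Working it through.** There is no figure in the plan to reproduce: the documents give no expected MI rate, no power and no hypothesis test for this endpoint. The check is mainly a reading of the passages side by side.

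**Step 1. Routes by which a postoperative MI can reach the endpoint**

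| Route | Where | What it needs | What it leaves out |
|---|---|---|---|
| Mandatory EKG and troponin | Table 6 footnote t | A cardiac ischemic AE | MI not recognised as such |
| Troponin on symptoms or concern | Appendix 2 footnote c | Clinical suspicion | Silent MI; EKG is not covered |
| Laboratory change recorded as AE | Section 9.2.1 | Investigator judges it clinically significant; no troponin threshold is stated | Rises overlooked or judged not significant; a new Q wave, which is not a laboratory value |
| SOC result entered in the eCRF | Section 9 | Site chooses to enter it | Anything not entered, with no deviation |
| CEC adjudication | Section 9.2.1 | A reported event that meets programmed criteria | Unreported events |

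The first three routes each depend on recognition, suspicion or judgement at the site. The fourth is voluntary. The fifth comes after the others. None is a systematic screen of data collected on every subject.

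**Step 2. Comparison with bleeding in the same plan.** Under Section 9.2.1, UDPB class is determined from data entered in the eCRFs, and every subject whose data meet Class 2, 3 or 4 goes to the CEC. Chest tube drainage and transfusions must be recorded (Section 9.2.6; Table 6 footnote m). Bleeding is thus classified from systematic data, and MI from site recognition.

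**Step 3. Illustration of size, on assumed rates.**
- Inputs: n = 57 per arm (Section 11.1). The true MI rates and the capture share s are assumptions, not in the documents, and s is taken as equal in both arms.
- Expected events per arm = 57 × p × s.
- Power is for an exact two-sided Fisher test at 0.05. It is used only as a yardstick, because no such test is planned for MI.

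| Assumed true rates (control v device) | s | Expected events | Fisher power |
|---|---|---|---|
| 8% v 24% | 1.0 | 4.6 v 13.7 | 56% |
| 8% v 24% | 0.7 | 3.2 v 9.6 | 36% |
| 8% v 24% | 0.4 | 1.8 v 5.5 | 14% |
| 10% v 20% | 1.0 | 5.7 v 11.4 | 23% |
| 10% v 20% | 0.7 | 4.0 v 8.0 | 14% |
| 10% v 20% | 0.4 | 2.3 v 4.6 | 5% |
| 5% v 10% | 1.0 | 2.9 v 5.7 | 8% |
| 5% v 10% | 0.7 | 2.0 v 4.0 | 4% |

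For example, 57 × 0.24 × 0.7 = 9.6. With equal capture the risk ratio is unchanged, but the expected difference in events shrinks in proportion to s: for 8% v 24%, 57 × 0.16 = 9.1 events at full capture and 9.1 × 0.7 = 6.4 at 70%.

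**Step 4. A related inconsistency.** Appendix 2 footnote c ties screening troponin to females of child-bearing potential. Table 6 requires it at Screening with no such limit. It is therefore unclear who has the baseline value against which a postoperative rise would be read.

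**The case against.** The strongest reply is that event-driven ascertainment is an open design choice with several safeguards. Footnote t is triggered by the occurrence of an ischemic AE. Troponin can be prompted by concern alone, before any AE is reported. A large troponin rise that the investigator considers clinically significant must be recorded as an AE. Subjects are observed daily for signs as well as questioned, so sedation alone does not block detection. All deaths within 30 days and all coronary revascularizations after the index procedure during follow-up go to the CEC, and monitors have access to the medical records. The MI definition and programmed criteria are in the CEC charter, which is not among these documents.

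Much of this stands, and it rules out two stronger readings. A reader might infer that the tests are required only after a site has reported an event, or that a subject with a large troponin rise in the chart can never reach the CEC. The documents support neither. A reader might also infer bias in favour of the device. That is not shown: surgical, anesthesia and ICU staff and the study coordinator are blinded (Section 6.3), and randomization is stratified by site (Section 6.1), so the loss is probably similar in both arms.

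The power figures also have limits. Section 11.8 describes safety analysis by summaries and listings, the rates and capture shares are assumed, and at 5% v 10% the trial would see little even with full capture. Full capture is not attainable either, since some sites may not test routinely.

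The safeguards nevertheless leave a residual gap. Each relies on someone at the site recognising or suspecting the event, or judging a result significant. The laboratory rule does not reach an EKG finding. Source verification under Section 13.5 checks what was entered, and an empty SOC field is compliant. A charter definition cannot be applied to results that are neither entered nor reported.

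**Conclusion.** The point holds in a limited form. MI that is overlooked, or judged not significant, can be missing from the endpoint even when the EKG or troponin evidence is in the chart. The probable consequence is lower counts in both arms and a masked difference in a descriptive, non-primary safety endpoint. The primary effectiveness endpoint is not affected.

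The size cannot be fixed from the documents, because the true MI rate, the share missed and the charter criteria are not given. The table above shows direction and order of magnitude only, assuming equal capture in both arms. With counts this small, a few missed events matter, so the change is worth making as a cheap improvement.

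**What to change.** 1. In Section 9 and Table 6, require that postoperative EKG and troponin results be entered in the eCRF whenever they are obtained during the index hospitalization, with the troponin upper reference limit and any new Q wave. The window should match the endpoint; the day-5 limit in footnote u belongs to the hematology, chemistry and coagulation rows.
2. Refer to the CEC every subject whose entered data meet the charter's MI criteria, whether or not an AE was reported, as is already done for UDPB class.
3. Report by arm the number of subjects with a postoperative EKG and with a postoperative troponin.
4. Reconcile Section 9, Table 6 footnote t and Appendix 2 footnote c, including the restriction on screening troponin that appears in footnote c but not in Table 6.
5. Describe the endpoint as MI ascertained from clinical recognition and available SOC tests.

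No test is added. The cost is data-entry time, a few eCRF fields and some extra CEC referrals. Sites that do not test routinely will still contribute no values, so variation between sites is reduced, not removed; items 3 and 5 make that visible.

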9.1. Procedures and Assessments by Study Phase

Subjects are considered enrolled in the study at the time which consent or assent (in the case of a proxy providing permission for an incapacitated subject) to participate in the study is provided. Details on the consent process are provided in [Section 15.3](#) and the ethics of consenting non-vulnerable and vulnerable (incapacitated) populations are detailed in [Appendix 3](#).

[figure not shown]
Subjects who do not meet study entry (inclusion/exclusion) criteria are screening failures and will exit the study. Treated subjects will be followed up through 30 days after the surgical procedure.

The start of the investigation is defined as the date of consent to enroll the first prospective subject. The end of the investigation is defined as the date of the last subject's last contact or assessment (whether scheduled or unscheduled).

The investigation is divided operationally into 6 phases:

- Screening Phase – the period between the time consent/assent is provided for study participation and the start of the surgical procedure with CPB
- Pre-CPB Phase – the period within 2 hours before start of the operation with CPB (time of skin incision). *Note: The Pre-CPB Phase may overlap with the Screening phase.*
- Operation Phase – the start of the surgical procedure (defined as skin incision) until chest closure.
- Post-CPB Phase – the period from the end of CPB up to admission to the Intensive Care Unit (ICU). *Blood sampling for drug removal obtained in the post-CPB phase should be drawn as soon as possible following the end of CPB, and no later than 30min after the subject has been disconnected from the CPB circuit.*
- Post-operation Phase – from admission to the ICU through Day 29 or the point of discharge from hospitalization, whichever is sooner. **Discharge from hospitalization** means the date of initial discharge from the hospital in which the cardiothoracic surgery was completed (i.e., index procedure) irrespective of discharge to home care, secondary care or other rehabilitation unit.
- Day 30 Evaluation Post-Cardiothoracic Surgery – The subject status on postoperative day 30 will be evaluated by telephone contact, in-person follow-up visit, or review of medical records. Assessment of mortality (i.e., vitals status), blood product transfusions, and other adverse events will be performed.

An overview of the investigation design is shown in [Figure 5](#).

* Pre-CPB phase may overlap with the Screening Phase.

Figure 5. Investigation Schematic

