4.3. Study Outcomes

4.3.1. *Primary Effectiveness Endpoint:*

- Ranked composite of surgical and early post-surgical bleeding events:
 - 1) Fatal bleeding events occurring within 48hrs post-index procedure,
 - 2) UDPB ≥ 2 perioperative bleeding, and
 - 3) 24-hour chest tube drainage volume (mL).

Refer to [Table 1](#) for details of the UDPB classification of bleeding events.

4.3.2. *Key Secondary Effectiveness Endpoints:*

- Percent change in pre-CPB vs. post-CPB blood apixaban levels as measured by liquid chromatography/tandem mass spectrometry (i.e., Δ [Apixaban]).
- Percent change in pre-CPB vs. post-CPB blood rivaroxaban levels as measured by liquid chromatography/tandem mass spectrometry (i.e., Δ [Rivaroxaban])

4.3.3. *Additional Secondary Effectiveness Endpoints:*

- 24-hour chest tube drainage volume
- Total platelet transfusions during the index hospitalization (volume and units)
- Total PRBC transfusions during the index hospitalization (volume and units)
- Total UDPB events (by class)
- All surgical re-exploration for excessive bleeding
- Total fatal perioperative bleeding events

4.3.4. *Exploratory Endpoint(s):*

- Area under the concentration time curve (AUC), for intraoperative apixaban or rivaroxaban pharmacokinetic (PK) concentration
- Operative time (measured from start of skin incision to completion of chest closure)
- Duration of ICU stay
- Duration of hospital stay
- 30-day hospital readmissions

4.3.5. *Primary Safety Endpoint:*

- The primary safety endpoint of this trial is to evaluate the product safety profile through the GCP-level assessment of AEs during the study period.

4.3.6. *Additional Safety Endpoints:*

- 30-day cardiac mortality
- 30-day all-cause mortality
- Postoperative stroke during the index hospitalization
- Postoperative myocardial infarction (MI) during the index hospitalization
- Urgent postoperative coronary revascularization during the index hospitalization
- Postoperative venous thromboembolic events (VTE) during the index hospitalization
- Serious device-related adverse events

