Informed consent shall be obtained in writing from the subject, or their legally authorized representative and the process shall be documented before any procedure specific to the clinical

investigation is applied to the subject; additional details are provided in [Appendix 3](#). If during the course of the study assessments, a subject is found not to be eligible for inclusion in the study, the subject or their representative should be notified and the reason for ineligibility documented on the screening log/form.

The general process for obtaining informed consent shall:

- Ensure that the principal investigator or his/her authorized designee conducts the informed consent process
- Include all aspects of the clinical investigation that are relevant to the subject's decision to participate throughout the clinical investigation
- Avoid any coercion or undue improper influence on, or inducement of, the subject to participate
- Not waive or appear to waive the subject's legal rights
- Use native non-technical language that is understandable to the subject
- Provide ample time for the subject to read and understand the Informed Consent Form (ICF) and to consider participation in the clinical investigation
- Include personally dated signatures of the subject and the principal investigator or an authorized designee responsible for conducting the informed consent process;
- Provide the subject with a copy of the signed and dated ICF and any other written information
- Ensure important new information is provided to new and existing subjects throughout the clinical investigation

4.4.4. Subject Withdrawal/Discontinuation:

Investigation subjects may withdraw voluntarily from the research investigation for any reason and at any time during the course of the investigation. Subjects may also be discontinued from the investigation for the following medical or administrative reasons:

- At the request of the Investigator, if he/she feels that the subject can no longer fully comply with the requirements of the study or if any of the study procedures would not be in the best interest of the subject.
- Termination of the study by the Sponsor.
- Non-compliance with CIP procedures.
- The subject is lost to follow-up. A subject will be considered “lost to follow-up” when all the following criteria are met:
 - Failure to complete the 30-day follow-up visit or follow-up telephone call without due cause; and

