9.1.3. Postoperative phase through 30-day evaluation

Subjects will undergo scheduled study procedures as indicated in the Schedule of Assessments in [Appendix 4](#) until the point of discharge from index hospitalization. A Follow-up Evaluation will be performed 30 days after the index operation for vital status/mortality check. This can be done via telephone contact, in-person follow-up visit, or review of medical records.

Postoperative Antithrombotic Management:

Approaches to antiplatelet and anticoagulation management during the study are listed below and summarized in [Table 5](#). All subjects on preoperative aspirin should be maintained on the same therapy through-out the study. Additionally:

1. Any ACS subjects or those with recent coronary stent placement who *cannot* discontinue DAPT (i.e., clopidogrel, ticagrelor, etc.) for the recommended *preoperative washout* period will be excluded from study participation. Initiation of DAPT in the *postoperative* period is at the discretion of the investigator, or per their institutional protocols.
2. Timing of resumption for DOAC therapy in the postoperative period will be at the discretion of the investigator, based on the indication for anticoagulation and the anticipated bleeding risk.

Postoperative anticoagulation for venous thromboprophylaxis in all subjects should be administered according to standardized institutional protocols.

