9.2. Safety and Tolerability Assessments

9.2.1. Adverse Events

Throughout the study, the Investigator or designee will determine adverse event (AE) occurrences. AE definitions, assignment of severity/seriousness/causality, and procedures for reporting SAEs, SADEs, and UADEs are detailed in [Appendix 1](#).

The condition of each subject will be monitored from the time of signing the Informed Consent Form (*assent* if signed by the legally authorized representative, or *consent* if signed by the individual) to the postoperative day 30 assessment. Subjects will be observed for any signs or symptoms and if possible, asked about their condition by open questioning, such as “How have you been feeling since you were last asked?”, at least once each day while in hospital and at each investigation visit. Subjects will also be encouraged to spontaneously report AEs occurring at any other time during the investigation.

If an AE occurs, appropriate diagnostic and therapeutic measures are to be taken and the investigation treatment may be discontinued if deemed clinically necessary. Follow-up evaluations of the subject are to be performed until the subject recovers or until the clinical Investigator considers the situation to be no longer clinically significant.

Adverse events are monitored and recorded on the AE form of the eCRF. In absence of a specific diagnosis, an individual AE form must be filled in for each sign or symptom. Changes from baseline laboratory values which are abnormal values and that are classified as clinically significant by the investigator (e.g., requiring medical intervention) must be recorded as AEs.

Persistent AEs will be entered once in the eCRF until they are resolved; a new event must be documented if deterioration occurs. These AEs will be carefully monitored. If an AE is still not resolved at the end of the investigation, this will be documented as “ongoing.” For recurrent AEs (i.e., AEs of the same nature, but with a different date of onset), an individual AE form must be completed for each of them.

Bleeding event AEs

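### The day-30 evaluation may be completed from medical records alone, with no contact attempt and no dated proof of status, so post-discharge deaths, adverse events and readmissions can be under-ascertained

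*Combined protocol and SAP*

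**What the plan says.** Section 9.1 allows the day-30 status to be "evaluated by telephone contact, in-person follow-up visit, or review of medical records". It then gives the content: "Assessment of mortality (i.e., vitals status), blood product transfusions, and other adverse events will be performed". Section 9.1.3 lists the same three routes ("This can be done via telephone contact, in-person follow-up visit, or review of medical records") but states a narrower purpose: "A Follow-up Evaluation will be performed 30 days after the index operation for vital status/mortality check".

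In Section 4.3, the endpoints that reach to day 30 are the primary safety endpoint (adverse events over the study period), "30-day all-cause mortality", 30-day cardiac mortality, serious device-related adverse events, and the exploratory endpoint "30-day hospital readmissions".

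Section 4.4.4 defines loss to follow-up by two conditions that must both hold: "Failure to complete the 30-day follow-up visit or follow-up telephone call without due cause", and three documented unsuccessful contact attempts. Section 9.2.1 has subjects "asked about their condition by open questioning", where possible, daily in hospital and at each study visit. Section 11.8 reports adverse events as frequency and percentage by arm. Section 11.7 assumes 5% missing effectiveness and safety data, plans sensitivity analyses, and leaves the detail to the SAP.

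**The concern.** Record review is an equal alternative to speaking with the subject, although a chart can show only what reached it. Section 9.1 counts transfer to secondary care or rehabilitation as discharge, so a subject's later records may sit at another institution. A site may consult the records it holds, find no entry after discharge, and complete the evaluation without a call.

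What is at stake is the completeness of the 30-day safety picture in a small trial. An event that is not found this way leaves no trace: the subject is not flagged as lost or as missing, so the planned missing-data analyses have nothing to act on.

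**Working it through.** The point rests mainly on reading the rules together. The arithmetic only gives scale.

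1. **Is there another scheduled look after discharge?** No. The post-operation phase in Section 9.1 ends at discharge (or day 29 if sooner), and the daily rows of Table 6 stop at discharge under note s. The adverse-event row is marked for days 5-29 without that note, so recording continues in principle, but no contact is scheduled until day 30.

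2. **Are the three routes conditioned?** No. Neither Section 9.1 nor Section 9.1.3 gives an order of preference, requires a prior contact attempt, says whose records count, requires records from other hospitals, or asks for an entry dated on or after day 30.

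3. **What happens to a subject closed from the chart with no call?**
   - *Section 4.4.4:* not lost to follow-up, because three failed contact attempts are needed and none was made.
   - *Section 9.2.1:* no open questioning takes place, since there is no visit.
   - *Adjudication (Sections 7.2 and 9.2.1):* the Clinical Events Committee can act only on events that reach the study.
   - *Section 11.7:* the subject looks complete, so is not identified as missing.
   - *Section 11.8:* incidence is a crude percentage, with no category for unknown status. By default the subject sits in the denominator without an event.

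4. **Do the sections agree on content?** Not fully. Section 9.1.3 describes a survival check. Section 9.1 adds transfusions and adverse events. Table 6 marks adverse events, bleeding and concomitant medications at day 30 but not blood products, which note m records only through discharge. Readmission is an endpoint, yet neither section names it and it has no row in Table 6.

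5. **Scale.** The only stated figure that bears on completeness reproduces: 120 × (1 − 0.05) = 114, and 114 / 2 = 57 per arm. One missed event changes an arm's rate by 1/57 = 1.75 percentage points.

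6. **Illustration; every input is assumed.** Missed events per arm = 57 × p × f × r × s, where p is the true event risk, f the share of events outside the index hospital, r the share of subjects followed by records only, and s the share of those outside events that are missed.

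| p | f | r | s | Missed per arm | Observed rate |
|---|---|---|---|---|---|
| 5% | 10% | 25% | 50% | 0.04 | 4.94% |
| 10% | 30% | 50% | 50% | 0.43 | 9.25% |
| 20% | 50% | 100% | 100% | 5.7 | 10% |

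For the middle row: 57 × 0.10 × 0.30 × 0.50 × 0.50 = 0.43, and 10% − 0.75% = 9.25%. The range of 0.04 to 5.7 shows how little the documents constrain the answer.

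7. **Effect of equal loss on a difference.** If both arms lose the same share L of events, the risk difference shrinks by the factor (1 − L). With assumed true rates of 5% and 20% and L = 25%, the observed rates are 3.75% and 15%, so the difference is 11.25 points instead of 15.

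**The case against.** The strongest case is that the plan intends real follow-up. Table 6 requires adverse events, bleeding and concomitant medications at day 30. Section 9 makes an uncompleted required assessment a protocol deviation, and Section 13.2 lists failure to conduct follow-ups as one. Section 6.3.1 makes the blinded coordinator responsible for ensuring that follow-up visits are scheduled. Section 9.2.1 encourages spontaneous reporting, and the lost-to-follow-up definition treats contact as the normal route. On this view, closing a subject from an empty chart is a lax reading.

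The intent is clear, and a careful site will call. But these provisions do not close the gap: Section 9.1 makes record review an accepted way to complete the evaluation, so a site that uses it has not plainly deviated.

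Several stronger readings are tempting and are not supported:

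- *That unrecorded events are scored as non-events.* No section says so. It is the default result of crude percentages with no rule for unknown status, and the SAP could still prevent it.
- *That only the index hospital's chart is consulted.* The text says medical records without restriction. The defect is that outside records are not required.
- *That the trial's thrombotic endpoints are lost.* Stroke, myocardial infarction, urgent revascularization and venous thromboembolism are endpoints during the index hospitalization only. Later events of these kinds count as adverse events and go to adjudication if reported.
- *That one or two lost events would remove a signal made of few late events.* If 30% of subjects were closed by chart and half of their events were treated elsewhere (both assumed), 0.30 × 0.5 = 15% of post-discharge events would be missed. An expected loss of one event then needs about 1/0.15 = 6.7 events, and of two about 13.3. That is not a handful.
- *That the loss favours the device.* The study coordinators who enter follow-up data are blinded, so there is no evident reason for the loss to differ by arm.

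**Conclusion.** The point holds as an ascertainment gap and a cheap improvement. As written, the day-30 evaluation can be completed with no contact attempt, no outside records and no dated evidence of status, and such a subject falls outside the lost-to-follow-up definition. Post-discharge adverse events, 30-day all-cause and cardiac mortality, and exploratory readmission are exposed.

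The scope is limited. The primary effectiveness components (48 hours, first postoperative day, 24 hours), the drug-removal endpoints, the index-hospitalization transfusion endpoints, and the stroke, infarction, revascularization and thromboembolism endpoints do not depend on the day-30 route.

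The direction is probably towards lower absolute rates in both arms, with differences masked. This assumes that blinding of site staff keeps the loss balanced. The size cannot be derived, because the documents give neither a 30-day event rate nor the share of subjects who would be followed by records only.

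**What to change.** In Sections 9.1 and 9.1.3, require telephone or in-person contact with the subject or a proxy at postoperative day 30 (+5 days) for every discharged subject. The contact should cover vital status, readmission at any hospital, adverse events, bleeding and transfusion.

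Accept record review alone only when:

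- the subject is still an inpatient;
- a death is recorded;
- dated records document status on or after day 30; or
- three documented contact attempts have failed, using the rule already in Section 4.4.4.

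In the last case, record the last date known alive and treat later status as missing. Record on the eCRF which route was used.

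Align the purpose stated in Section 9.1.3 with Section 9.1 and Table 6, including the blood-products row, and give readmission a place in the schedule.

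The cost is about one call per discharged subject, by a route the plan already allows. A few more subjects will be reported as lost to follow-up.
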